11.5.3 Elevation of Liver Function Test Parameters

Mandatory Liver Function Testing

Liver function testing (ALT, AST, GGT, ALP, and total bilirubin) must be performed while subjects are receiving study drug treatment (Table 3-2). These blood samples will be processed and shipped immediately per the Laboratory Manual.

It is strongly recommended that subjects with new treatment-emergent ALT or AST elevations of $>3 \times \text{ULN}$ and clinical symptoms be followed closely, including repeat confirmatory testing performed by the central laboratory within 48 to 72 hours of the initial finding and subsequent close monitoring of ALT and AST levels, as clinically indicated.

If a subject cannot return to the site for liver function testing, a local laboratory may be used. Elevations in LFTs (as indicated above) at the local laboratory must be reported immediately to the medical monitor **and** the subject must have the tests repeated and sent to the central laboratory as soon as possible (ideally within 48 to 72 hours).

Study Drug Interruption

Study drug administration **must be interrupted** immediately, and the medical monitor must be notified if any of the following criteria is met:

- ALT or AST $>8 \times \text{ULN}$
- ALT or AST $>5 \times \text{ULN}$ for more than 2 weeks
- ALT or AST $>3 \times \text{ULN}$, in association with total bilirubin $>2 \times \text{ULN}$ and/or clinical jaundice

A thorough investigation of potential causes should be conducted, and the subject should be followed closely for clinical progression.

If no convincing alternative etiology (e.g., acetaminophen use, viral hepatitis, or alcohol ingestion) for the elevated transaminases is identified, regardless of whether ALT or AST levels have improved, study drug treatment must be discontinued, in consultation with the Vertex medical monitor or authorized designee. Subjects in whom treatment is discontinued for elevated transaminases should have their transaminases monitored closely until levels normalize or return to baseline.

Resumption of Study Drug

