9 STATISTICAL ANALYSIS

9.1 General Considerations

The Schedule of Assessments is provided in Appendix A.

All individual subject data for those randomized or exposed to study drug will be presented in data listings.

Continuous variables will be summarized using the following descriptive summary statistics: the number of subjects (n), mean, standard error (SE), standard deviation (SD), median, minimum value (min), and maximum value (max). The precision of the measurement for each continuous variable will be used to determine the number of decimal places to present in tables, figures, and derived listings. Minimum and maximum values will be reported with the same precision as the units of measure. The mean and median will be reported to 1 greater decimal place, and the SE and SD will be reported to 2 additional decimal places. Any values that require transformation to standard units (metric or SI) will be converted with the appropriate corresponding precision.

Categorical variables will be summarized using counts and percentages. Percentages will be presented to 1 decimal place.

Baseline Value: Unless otherwise specified, the baseline value will be defined as the most recent non-missing measurement (scheduled or unscheduled) collected prior to the initial administration of study drug. Baseline CPET data will be collected on Day 1 prior to the initial administration of study drug. Unscheduled visit measurements will be included for derivation of baseline. For actigraphy variables, baseline data will be defined as the mean of the data collected for the 7 days immediately preceding Day 1 (Day -7 to Day -1) during the Screening Period.

Absolute Change from baseline will be calculated as Post baseline value - Baseline value.

Relative change from baseline will be calculated and expressed in percentages as $100 \times \frac{(\text{Post baseline value} - \text{Baseline value})}{\text{Baseline value}}$.

Unscheduled Visits: Unscheduled visit measurements will be included in listings, for derivation of visit windows and computation of baseline/last on-treatment visit, and for the analysis of maximum/minimum on-treatment values and maximum/minimum changes from baseline values.

Visit Windows: Appendix C defines the visit window mapping rules to derive the analysis visits.

Repeated observations within the same visits window

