- For all efficacy parameters, if there are multiple measurements within a visit window, the record at the scheduled visit will be used. If there are no measurements at the scheduled visit, then 1) the record closest to the target day will be used; or 2) if there are multiple records with the same distance to the target day, the latest record will be used.
- For all safety parameters, if there are multiple measurements within a visit window, then 1) the record closest to the target day will be used; or 2) if there are multiple records with the same distance to the target day, the latest record will be used.

BMI will follow visit window rules for efficacy parameters when being considered as an efficacy endpoint.

Incomplete/Missing data will not be imputed, unless otherwise specified; i.e., all missing values will remain as missing in all statistical analyses and listings, unless otherwise specified. Missing post-baseline values will not be imputed for efficacy analysis conducted

using a mixed model for repeated measures (MMRM) approach, which makes use of all available data even if a subject has missing data at some post-baseline visits.

Outliers: No formal statistical analyses will be performed to detect and/or remedy the presence of statistical outliers.

Repeated Observations: Measurements recorded at different time points are defined as repeated observations. If an assessment has planned repeated measurements, then statistical summaries will present all planned time points, as appropriate.

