9.4.2 Clinical Laboratory

For the laboratory measurements, the raw values and change from baseline values of the continuous hematology and chemistry results will be summarized in SI units by treatment group at each scheduled time point. For hematology and chemistry, the number and percentage of subjects with abnormal low ($<LLN$) value and with abnormal high ($>ULN$) value at each scheduled time point will be summarized.

The number and percentage of subjects with at least one potentially clinically significant (PCS) event for liver enzyme during the treatment-emergent period will be summarized. The PCS criteria are provided in Appendix F.

For all LFT results (alanine aminotransferase [ALT], aspartate aminotransferase [AST], serum alkaline phosphatase [ALP], Gamma-glutamyl transferase [GGT] and total bilirubin), the following analyses will be conducted:

- For each of the LFTs, mean values (and 95% confidence interval) will be plotted against visit, and box plot of LFT value/ULN will be plotted against visit.
- The incidence of PCS LFTs during the treatment-emergent period according to the baseline status will also be summarized by treatment group (only worsening of the shift from baseline will be presented).
- A listing of subjects with elevated LFT results during the treatment-emergent period will be presented. The listing will include all parameters of the LFT assessment at all visits.

Results of urinalysis and the serum pregnancy test will be listed in individual subject data listings only. In addition, a listing containing individual subject hematology, chemistry, and

coagulation values outside the reference ranges will be provided. This listing will include data from scheduled and unscheduled time points.

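### For safety data the SAP takes the record closest to the target day and gives the scheduled visit no priority, so a recheck prompted by an abnormal result can replace that result in by-visit liver-test and blood-pressure summaries

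*SAP*

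**What the plan says.** SAP 9.1 gives two selection rules, one after the other, for several records in one visit window.

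- **Efficacy:** "For all efficacy parameters, if there are multiple measurements within a visit window, the record at the scheduled visit will be used". Closeness to the target day matters only if that record is missing.
- **Safety:** "For all safety parameters, if there are multiple measurements within a visit window, then 1) the record closest to the target day" is used. After that, "if there are multiple records with the same distance to the target day, the latest record will be used". The scheduled visit has no priority.

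The same section admits unscheduled records: "Unscheduled visit measurements will be included in listings, for derivation of visit windows and computation of baseline/last on-treatment visit".

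Appendix C (Table 12-3) sets targets of Day 85 (Week 12) and Day 169 (Week 24), with windows (1, 92] and [93, 176]. Vital signs and liver function tests are among the assessments it names.

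The outputs that use one record per visit are:

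- **SAP 9.4.2:** chemistry and haematology raw values and changes, and counts below LLN or above ULN, for which the "value at each scheduled time point will be summarized"; also the liver-test mean plots and box plots by visit.
- **SAP 9.4.3:** systolic and diastolic blood pressure by visit, as a table only.

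Protocol 11.5.3 strongly recommends close follow-up of new ALT or AST elevations above 3 x ULN with clinical symptoms, including "repeat confirmatory testing performed by the central laboratory within 48 to 72 hours of the initial finding".

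**The concern.** Rechecks are not a random sample of extra measurements. They are taken because a result was abnormal, and above the stricter thresholds in protocol 11.5.3 study drug may already have been interrupted when the second sample is drawn. A rule that lets the recheck stand in for the result that triggered it therefore selects records on the outcome.

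If rechecks tend to be closer to normal, by-visit means and out-of-range counts would understate abnormalities, and more so in an arm that has more of them. With about 33 subjects per arm, one displaced subject can move an out-of-range percentage by about 3 points (1/33 = 3.0%). The SAP gives no reason for treating safety records differently from efficacy records.

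**Working it through.** The documents state no figure to reproduce, so the check applies the SAP rule to each permitted visit day.

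**Inputs**
- Target T: Day 85 or Day 169 (SAP Appendix C).
- Scheduled visit day d: T − 7 to T + 7, which is 15 days (schedule of assessments, ± 7 days).
- Window upper limits: Day 92 and Day 176 (SAP Appendix C).
- Recheck lag L: 2 to 3 days (protocol 11.5.3, 48 to 72 hours). Other lags are shown for range.
- Ties go to the latest record (SAP 9.1).

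**Formula**

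The recheck on day d + L is selected if |d + L − T| ≤ |d − T| and d + L lies inside the window. For L of at least 1 this reduces to d ≤ T − L/2. The window limit does not bind for these lags, because the days that qualify are all before the target.

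**Results for Week 12, T = 85, d = 78 to 92**

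| Lag (days) | Condition | Visit days on which the recheck is used | Fraction |
|---|---|---|---|
| 1 | d ≤ 84.5 | 78–84 | 7/15 = 47% |
| 2 | d ≤ 84 | 78–84 (six strictly closer, Day 84 by the tie rule) | 7/15 = 47% |
| 3 | d ≤ 83.5 | 78–83 | 6/15 = 40% |
| 6 | d ≤ 82 | 78–82 | 5/15 = 33% |
| 7 | d ≤ 81.5 | 78–81 | 4/15 = 27% |

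Week 24 gives the same fractions (for example Days 162–168 at a lag of 2 days).

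If visits cluster in Days 82–88 (an assumption), the fractions are 3/7 = 43% at 2 days, 2/7 = 29% at 3 days, 1/7 = 14% at 6 days and 0/7 at 7 days.

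A same-day repeat ties on distance. If time of day decides which record is latest, it replaces the first value on 15 of 15 days.

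**Example.** A scheduled Day 80 ALT above 3 x ULN is 5 days from target. A recheck on Day 83 is 2 days from target. The Day 83 value goes into the Week 12 table and plots.

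**Under the efficacy rule.** With the scheduled record first, an available scheduled result is displaced on 0 of 15 days at any lag.

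All these fractions are conditional on a recheck having been done.

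**The case against.** The best defence is that the closest-day rule is prespecified, blind to treatment and applied only to descriptive safety data. Several parts of this case stand.

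- **Other outputs keep the value.** The any-time liver and vital-sign PCS tables (SAP 9.4.2, 9.4.3, Appendix F) do not depend on the selection rule. The rechecks named in protocol 11.5.3 follow ALT or AST above 3 x ULN, which is itself a PCS criterion. SAP 9.1 also admits unscheduled values to maximum and minimum on-treatment analyses, and the out-of-range laboratory listing includes unscheduled results.
- **Other laboratory tests.** Laboratory PCS criteria cover liver tests only, so a reader might infer that by-visit tables are the only summary for the rest. The documents do not support that. Clinically significant abnormal results become adverse events (protocol 11.5.2, 12.3.4.2, 13.1.1.2) and enter the adverse event tables, and the maximum/minimum provision and listings apply too. Appendix C as extracted names only liver tests among laboratory parameters, so windowing of other tests is not explicit.
- **Blood pressure.** No timed recheck is set for vital signs. Protocol 11.5.4 only allows symptom-directed assessments at discretion.
- **Lag.** The 48 to 72 hours run from the first abnormal result. If that means the date the central laboratory result is available, and turnaround is 1 to 3 days (an assumption), the lag is 3 to 6 days. The fractions are then 40% to 33% under uniform visits and 29% to 14% for Days 82–88.
- **Direction.** A confirmatory repeat may confirm or exceed the first value.

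One argument does not stand. The phrase about scheduled time points in SAP 9.4.2 and 9.4.3 could be read as scheduled records only. But SAP 9.1 brings unscheduled records into the windows and gives a rule for choosing among them. If scheduled-only was intended, the wording still needs correction.

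**Conclusion.** The point holds as a defect in record selection, limited to by-visit liver-test means, out-of-range counts and plots and the by-visit blood-pressure table. Same-day repeats apart, a later recheck can displace the scheduled value only when the visit falls before the target day.

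Given a recheck 2 to 3 days after the visit and visit days uniform over target ± 7, displacement occurs on 7/15 to 6/15 of visit days. Longer lags or visits clustered near the target lower this, to zero at a 7-day lag with visits in Days 82–88.

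A reader might take 40% to 47% as the share of subjects or values affected, or conclude that the arm difference is shown to be biased toward none. Neither follows. The documents give no recheck frequency and no distribution of repeat values. The size of any bias is unknown, and a shift toward normal is likely but unproven. No efficacy result is touched.

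**What to change.** In SAP 9.1, give safety parameters the same order as efficacy parameters: the scheduled-visit record first, then the record closest to the target day only when no scheduled record exists in the window, with the present tie rule. Appendix C could also state which windows apply to laboratory tests other than liver tests.

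Do not switch the by-visit LLN/ULN counts to the worst value in the window. The windows span Days 2–92 and 93–176, that is 91 and 84 days. A worst-value count would become an any-time count over 12 to 13 weeks, would rise with the number of tests done, and would use different records from the means beside it.

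The cost is one sentence and minor programming before data lock. The small downside is that the record used may sometimes lie slightly farther from the target day.

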8.1.3 Follow-up

Subjects will have a Safety Follow-up Visit 4 weeks (± 7 days) after the last study drug dose. Safety Follow-up Visit assessments are listed in [Table 3-2](#). When the Safety Follow-up Visit is complete, the subject has completed the study.

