8.1.4 Early Termination of Treatment

If the subject prematurely discontinues study drug, an Early Termination of Treatment (ETT) Visit will be scheduled as soon as possible after the subject decides to terminate study drug. Subjects who prematurely discontinue study drug will also complete the Safety Follow-up Visit, approximately 4 weeks ± 7 days after their last dose of study drug. The assessments performed at the Safety Follow-up Visit are listed in [Table 3-2](#).

If the ETT Visit occurs 3 weeks after the last dose of study drug or later, then the ETT Visit will replace the Safety Follow-up Visit, and a separate Safety Follow-up Visit will not be required.

If the subject withdraws consent for the study, no further evaluations will be performed, and no additional data will be collected. Vertex Pharmaceuticals Incorporated (Vertex) may retain and continue to use any data collected before such withdrawal of consent.

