Appendix B Precisions of Summary for Continuous Variables

Continuous Variables

Table 12-2 Precision of Special Summary Statistics for CF Studies

Variables	Statistics	Decimal Places
CPET Related variables	Mean, LS mean, 95% CI	1
Percent Predicted FEV ₁	Mean, LS mean, 95% CI	1
CFQ-R	Mean, LS mean, 95% CI	1
BMI	Mean, LS mean, 95% CI	1
PHQ-8/GAD-7	Mean, 95% CI	1
Demographics	Mean, 95% CI	1
Actigraphy	Mean, 95% CI	1

The precision of the Safety Lab Data will follow the latest standard from the Biometrics Standardization Committee.

The precision of the measurement in raw data for other continuous variables will be used to determine the number of decimal places to present in tables, figures, and derived listings. Minimum and maximum values will be reported with the same precision as the units of measure. The mean and median will be reported to 1 greater decimal place, and the SD and SE will be reported to 2 additional decimal places.

Any values that require transformation to standard units (metric or International System [SI]) will be converted with the appropriate corresponding precision.

Appendix C Analysis Visit Window Mapping Rules for Safety and Pharmacodynamic and Actigraphy Measurements

Table 12-3 Visit Window Mapping Rules for Safety and Pharmacodynamic and Actigraphy Measurements

Assessments	Visit	Target Study Day	Visit Window (in study days)
• CPET related	Week 12	85	(1, 92]
•	Week 24	169	[93, 176]
• Spirometry	Safety follow up week 28	197	[177, 204]
•			
• CFQ-R/PHQ-8/GAD-7			
•			
• Weight and Height			
•			
• Vital Signs			
•			
• Actigraphy*			
•			
• Labs – Liver Function Test			

* Baseline actigraphy data will be the average of the corresponding actigraphy data 7 days prior to the Day 1 visit (Day -7 to Day -1). The same rule applies to actigraphy data collected at week 12 and week 24, where the average of the corresponding actigraphy data 7 days prior to the target day visit (target study Days 85 and 169 will be used for these two visits). Due to a window of ± 7 Days for each of these visits, the actual 7-day interval from which actigraphy data is used may vary from subject to subject.

Appendix D Coefficients for Hankinson and Wang Methods for Calculating Predicted Spirometry Parameters

Percent predicted FEV₁ is the ratio of FEV₁ (L) to the predicted FEV₁ (L), expressed as a percentage. The predicted FEV₁ (L) will be calculated using the Hankinson¹ and Wang² standards.

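### SAP Table 12-3 places the Safety Follow-up Visit by study day, so for most early stopping times its off-drug values are summarised as Week 12 or Week 24, and some compliant completer visits fall in no window

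*SAP*

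**What the plan says.** Protocol Section 8.1.3 anchors the visit on the last dose: "Subjects will have a Safety Follow-up Visit 4 weeks (± 7 days) after the last study drug dose". For subjects who stop early, Section 8.1.4 says the ETT "Visit will be scheduled as soon as possible after the subject decides to terminate study drug", with no day limit. "If the ETT Visit occurs 3 weeks after the last dose of study drug or later", it replaces the Safety Follow-up Visit. Section 8.1.2 keeps early stoppers in the study only through follow-up, so no later Week 12 or Week 24 visit is planned for them.

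The SAP works on a different clock. Section 9.1 states that "Appendix C defines the visit window mapping rules to derive the analysis visits". Table 12-3 there uses study days only:

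- Week 12: target 85, Days 2-92
- Week 24: target 169, Days 93-176
- "Safety follow up week 28": target 197, Days 177-204

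The table covers vital signs, weight and height, and liver function tests, among others. Where several safety records share a window, Section 9.1 applies this rule: "For all safety parameters, if there are multiple measurements within a visit window, then 1) the record closest to the target day" is used, and ties go to the latest record. Neither place exempts ETT or follow-up records.

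**The concern.** A follow-up visit timed from the last dose lands in Days 177-204 only if the subject stayed on drug until near Week 24. For someone who stops earlier, it lands in the Week 12 or Week 24 window. Values taken about four weeks off drug then stand as that visit's result, and they may take the place of the ETT value taken nearer to treatment.

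The outputs at stake are those built by visit. SAP Section 9.4.2 calls for laboratory values, changes, the percentages outside the normal range, mean plots of liver tests and box plots of liver tests relative to the upper limit of normal. Section 9.4.3 calls for by-visit blood pressure. Neither restricts these summaries to on-treatment records, although Section 9.4.4 does so for pulse oximetry. Table 12-3 maps weight in the same way, but Section 9.4.3 specifies no by-visit weight table.

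**Working it through.** **Reproducing Table 12-3.** Target day = 7 × week + 1 gives 85, 169 and 197 for Weeks 12, 24 and 28. Upper limit = target + 7 gives 92, 176 and 204. All match. The follow-up row is therefore Week 28 counted from first dose, which presumes a last dose at about Week 24.

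**Inputs.** Let L be the study day of the last dose. Follow-up falls on L + g, with g = 21 to 35 (Protocol 8.1.3). ETT falls on L + e. The documents give no value for e, so I assume e = 3 as the base case and vary it from 1 to 20; at 21 or more, ETT replaces follow-up. The earliest compliant Week 24 visit is Day 169 − 7 = 162, with the last dose the evening before (Protocol 10.2), so an early last dose means L = 1 to 160.

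**Where follow-up is mapped.** It goes to Week 12 if L + g ≤ 92 and to Week 24 if 93 ≤ L + g ≤ 176.

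| g | labelled Week 12 | labelled Week 24 | own window from |
|---|---|---|---|
| 21 | L ≤ 71 | L = 72-155 | L = 156 |
| 28 | L ≤ 64 | L = 65-148 | L = 149 |
| 35 | L ≤ 57 | L = 58-141 | L = 142 |

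**When follow-up displaces ETT (e = 3, g = 28).** ETT is in Week 12 for L ≤ 89 and in Week 24 from L = 90.

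- L = 1-64: both are in Week 12. The distances to Day 85 are |L − 57| for follow-up and 82 − L for ETT. The first is always smaller, so follow-up is kept.
- L = 65-89: ETT is Week 12 and follow-up is Week 24. Follow-up is mislabelled, but nothing is displaced.
- L = 90-148: both are in Week 24. The distances to Day 169 are |L − 141| and 166 − L. Follow-up is kept.
- L = 149-160: follow-up is in its own window.

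That is mislabelling on 148 of 160 possible last-dose days (92%) and displacement on 64 + 59 = 123 of 160 (77%). These are shares of days, not forecasts of subjects.

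Example: last dose Day 100, ETT Day 103 (66 days from 169), follow-up Day 128 (41 days from 169). Day 128 is reported as Week 24.

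**When ETT survives in a shared window.** For target T, ETT is closer only if L > T − (e + g)/2. Follow-up stays in the window only if L ≤ T + 7 − g. Both can hold only if g − e < 14. So ETT is kept only when the two visits are fewer than 14 days apart and follow-up falls in the last days of the window. With e = 14 and g = 21 this gives L = 68-71 and 152-155. For instance, at L = 70, ETT on Day 84 is 1 day from target and follow-up on Day 91 is 6 days away.

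**Completers.** Week 24 visit on Days 162-176, last dose on Days 161-175, follow-up from 161 + 21 = 182 to 175 + 35 = 210. The window ends at 204, so Days 205-210 are unmapped: 6 of 29 permitted days (21%). If visit day and follow-up interval are each uniform over their 15 permitted values (an assumption), 6 + 5 + 4 + 3 + 2 + 1 = 21 of 225 combinations (9%) are unmapped.

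**Scale.** The planned dropout is 10% of 33, or 3.3 per arm.

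**The case against.** The strongest reply is that little is lost. A reader might infer that the ETT value, including one that led to stopping, vanishes. It does not: it leaves one by-visit cell. It remains in the data listings, in the summaries of PCS liver and vital-sign values (which run over the treatment-emergent period, not visit windows) and in the elevated liver-test listing, which shows all visits. If it led to discontinuation, it should also appear in the adverse event tables and narrative listings. This stands.

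A reader might also infer a bias toward apparent safety in the arm with more discontinuations. That is plausible for abnormalities that reverse off drug. But the documents give no stopping-time distribution, no expected imbalance and no off-drug recovery data, and the safety analysis is descriptive.

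Nor does the SAP call the by-visit values on-treatment. Its treatment-emergent period runs to 28 days after the last dose, and ETT is itself normally off drug. It would also be too strong to say follow-up always wins, since a late ETT can be kept.

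Finally, one could read the summaries at scheduled time points as using nominal visits. Then ETT values would have no assigned place, and the vital-sign and liver-test rows of Table 12-3 would serve no purpose. The SAP needs clarifying on either reading.

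**Conclusion.** The mapping defect is real but narrow. Applied as written, the SAP labels off-drug follow-up values as Week 12 or Week 24 for last doses up to Day 148 (Day 155 with follow-up at 21 days, Day 141 at 35). Follow-up usually displaces ETT when the two share a window; the exact ranges, Days 1-64 and 90-148, rest on the assumed 3-day ETT.

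For early stoppers, about 3 per arm is a ceiling. It supposes that every planned dropout stops on an affected day and attends follow-up. Subjects who withdraw consent have no further visits, and an ETT that replaces follow-up displaces nothing. The completer gap is separate and needs no dropout. Its 21% is a share of calendar days, not of subjects; 9% holds only under uniform timing and would be lower if visits cluster near target.

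The primary endpoint is untouched, because the exercise test is not done at follow-up. BMI as an efficacy endpoint follows a different selection rule, and SAP Section 9.3 expressly admits measurements after discontinuation, so it lies outside this point.

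**What to change.** In SAP Appendix C, for safety parameters:

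1. Assign Safety Follow-up by nominal visit label, or by days since last dose (21-35, the protocol's own interval), whatever the study day.
2. Exclude those records from the Week 12 and Week 24 windows.
3. State that ETT records map to the study-day windows, and which slot an ETT takes when it replaces follow-up.

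In the base case this takes mislabelled last-dose days from 148 of 160 to 0 and displaced ETT records from 123 of 160 to 0. It also gives completer visits on Days 205-210 a place. I would not add a limit based on closeness to treatment: ETT has no fixed day and may fall up to 20 days after the last dose, so a limit could drop the records this change is meant to keep. An early ETT would still be labelled Week 12, since that window opens on Day 2.

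The cost is SAP wording and one programming rule before data lock, using visit labels and dose dates. No new data or visits are needed.
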